4.1. Baseline and Change from Baseline

4.1.1. Ureagenesis Baseline

Samples for ureagenesis are collected over a 4 hour-period at Screening and Day 1 to assess baseline ureagenesis. The screening assessment can be repeated if discrepant with subject's clinical status and severity.

Baseline of ureagenesis is defined as the average of Screening and Day 1 results. If the absolute difference of results between Screening and Day 1 is $\geq 25\%$ of normal rate of ureagenesis, then the Screening value will become the Baseline for ureagenesis.

If the Screening assessment has been repeated (i.e. unscheduled assessment) then the results from the unscheduled Screening visit will be used in lieu of the Screening results to determine the Baseline of ureagenesis.

This rule will be used to determine the visits to be included in the baseline derivation for each of the ureagenesis parameters (derived and reported).

For the non-AUC supplementary ureagenesis parameters, a baseline value is defined [REDACTED]

For $AUC_{0-240min}$ of absolute ^{13}C -urea and $AUC_{0-240min}$ of ^{13}C -Bicarbonate, the baseline value is defined [REDACTED]

For percent of normal $AUC_{0-240min}$ of absolute ^{13}C -urea, [REDACTED]

4.1.2. Other Parameters Baseline

For spot ammonia, plasma ammonia AUC_{0-24h} and urinary orotic acid AUC_{0-24h} the baseline value is defined [REDACTED]. For urinary orotic acid, a baseline value is defined [REDACTED]. For ammonia

scavenger therapy usage, the baseline value is defined [REDACTED]

For all other endpoints, the baseline value is [REDACTED]

4.1.3. Change from Baseline

All explicit references to change from baseline in this SAP refer to absolute change from baseline. Change from baseline is defined [REDACTED]

Percent change from baseline is defined [REDACTED]

If either the baseline or post-baseline value is missing, then the change from baseline and percent change from [REDACTED]

baseline value are set to missing. For each time point where change from baseline is evaluated for continuous variables, descriptive statistics will be displayed for the values at baseline, values at the given time point, and values for change from baseline at the given time point for those subjects who have data at both the baseline and the time point being evaluated.

4.2. Conversion of Days to Weeks or Months

The following conversion factors will be used to convert days into weeks or months: 1 week = 7 days, 1 month = 30.4375 days.

4.3. Duration

Duration will be calculated as stop date – start date + 1, unless otherwise specified.

Duration is calculated only when both dates are complete. Examples include duration of study participation, AE duration, and duration of oral steroid treatment.

4.4. Missing Data

Refer to the [Appendices](#) for imputation rules for partial and missing AE onset dates as well as partial and missing prior/concomitant medication start and end dates. For the adeno-associated virus serotype 8 (AAV8) binding antibody immunoglobulin (IgG), neutralizing antibodies to AAV8, amino acid panel, cell-mediated immune Response to AAV8 and OTC, chemistry, hematology (including coagulation panel), plasma ammonia (24 hours and spot), ureagenesis assay parameters, urinalysis, urinary orotic acid, vector genome determination (blood) and viral shedding (urine, saliva, and stool) laboratory data, quantitative results either below the lower limit of quantification (LLOQ) or above the upper limit of quantification (ULOQ) will be set to the LLOQ or ULOQ, respectively. Otherwise, no imputation of partial or missing values will be performed.

4.5. Multiple Testing

No formal adjustment for multiplicity will be performed.

4.6. Output Numbering

Numbering for tables, listings and figures will follow International Council for Harmonisation (ICH) E3 Guidelines.

4.7. Presentation of Continuous and Categorical Variables

Continuous data will be summarized using descriptive statistics (i.e., n, arithmetic mean, SD, median, minimum, and maximum). Categorical data will be summarized using event/subject count and percentage (n, %) in each category. Percentages will generally be reported to one decimal place. For descriptive statistics of all numeric variables, unless otherwise specified, the minimum and maximum will be displayed to the same level of precision as reported. Mean and median will be displayed to one level of precision greater than the data collected. SD will be displayed to two levels of precision greater than the data collected. P-values will be rounded to three decimal places. If a p-value is less than 0.001,

it will be reported as “<0.001.” If a p-value is greater than 0.999, it will be reported as “>0.999.”

When count data are presented, the percentage will be suppressed when the count is zero in order to draw attention to the non-zero counts. A row denoted “Missing” will be included in count tabulations where specified in the shells to account for dropouts and missing values. The denominator for all percentages will be the number of subjects within the analysis set of interest, unless otherwise specified.

4.8. Randomization, Stratification, and Blinding

This is an open label study, so there is no blinding of DTX301 dose, stratification, or randomization.

4.9. Sample Size

The study is expected to enroll up to 18 subjects. Three subjects will be enrolled into cohort 1 and then sequentially into cohorts of a minimum of 2 to 3 subjects. This sample size consideration is consistent with the sample size of other studies of similar design but is not based on a power calculation.

4.10. Significance Level

Unless otherwise specified, all testing of statistical significance will be 2-sided, and all p-values less than or equal to 0.05 will be considered statistically significant. Similarly, all confidence intervals (CIs) will be two-sided with a significance level of 5%.

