| | 
consideration if excluded per the rule for deriving the baseline value for the rate of ureagenesis. Added that derived and reported ureagenesis parameters will be summarized.
 
• Section 4.1.2, Other Parameters Baseline: Added spot ammonia and urinary orotic acid AUC_{0-24hr}.• Section 4.1.3, Change from Baseline: Updated the formula for calculating percent change from Baseline.• Section 4.9, Sample Size: Updated to align with Protocol Amendment 5.• Section 4.14, Unscheduled Visits: Added summaries of worst postbaseline value for hematology, chemistry, urinalysis, and amino acid parameters. Added that unscheduled visits will be included in figures for individual subjects.• Section 5.1, COVID-19: Added that no changes to planned analyses due to the impact of COVID-19 were made. Added pandemic start and end dates for participating countries.• Section 5.2, Disposition: Added that all disposition-related information for enrolled subjects will be listed.• Section 6.1, Demographics: Added that Screening and Baseline weight will be summarized. Added that the number of subjects by age category will be displayed. Added that all demographic data and baseline characteristics for subjects in the Safety Set will be listed.• Section 6.2, Medical History: Added that medical history data will be sorted in alphabetical order by System Organ Class and that Preferred Terms will be sorted in descending order by frequency within each System Organ Class. Added that medical history data will be listed.• Section 6.3, OTC Deficiency Medical History: Time since OTC deficiency became stable and time since stable dose of ammonia scavenger therapy will be reported in weeks instead of years. OTC deficiency medical history data for subjects in the Safety Set will be listed.• Section 7.1 Prior and Concomitant Medications: Prior and concomitant medications for subjects in the Safety Set will be listed.• Section 7.1.1, Prior Medications and Section 7.1.2, Concomitant Medications: Medications will be sorted in descending order by ATC level 4 term based on counts in the overall column.• Section 7.3, [1-¹³C]Sodium Acetate: Added section. Details related to [1-¹³C]sodium acetate administration for subjects in the Safety Set will be listed.• Section 8.1, Rate of Ureagenesis: Specified that MMRM outputs will include estimates for between-DTX301 dose (overall and by visit) comparisons. Removed summary statistics for rate of ureagenesis and longitudinal plot of change from Baseline to 4 hours postdose in rate of ureagenesis. Removed Yudkoff 2017 reference.• Section 8.2, Plasma Ammonia Area Under the Curve from Time 0 to 24 Hours: Summary statistics and listings will include time-normalized plasma ammonia AUC_{0-24hr}, which will be calculated by dividing AUC by the actual number of minutes between the 0- and 24-hour time points and multiplying by 60. Added the geometric mean, CV%, and geometric CV% for plasma ammonia AUC_{0-24hr} and time-normalized plasma ammonia AUC_{0-24hr} by visit. Added the mean and standard deviation for the logarithmic transformation of plasma ammonia AUC_{0-24hr} and time-normalized plasma ammonia AUC_{0-24hr}. Added a linear MMRM to provide a comparison vs Baseline of the logarithmic transformation of plasma ammonia AUC_{0-24hr} for each DTX301 dose. Updated the list of figures to be generated. |

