| 
Version 4.0 (25 November 2021)
 | 
 • Section 3.1, Overall Study Design and Plan: Updated the priority of enrollment for Cohort 4. • Section 8.1, Rate of Ureagenesis: Removed OTC genotype from the fixed effects in the MMRM model. • Section 8.2, Plasma Ammonia Area Under the Curve from Time 0 to 24 Hours: Geometric summary statistics will be provided overall, by cohort, and for Cohorts 3 and 4 combined. A linear MMRM will provide a comparison of the logarithmic transformation of plasma ammonia AUC_{0-24hr} for each DTX301 dose vs the lowest dose and at each visit vs Baseline. Removed OTC genotype from the fixed effects and baseline results as a continuous covariate in the MMRM model. • Section 8.3.8, Baseline Disease Management: Added definitions of Responder and Complete Responder for future development. • Section 8.3.9, Dietary Protein Prescription: In addition to total daily dietary protein intake, intact food protein and medical food protein will be summarized. Counts and percentages of subjects with type of change and of subjects on unrestricted protein diet will be generated. • Section 9.4, DTX301 Vector Genome Determination and Viral Shedding: Baseline value, highest value/timepoint, and timepoint of third consecutive negative results will be provided for each subject and sample type. Median values over time by cohort and sample type will be presented in a figure. Longitudinal displays over time by cohort for each subject and sample type will be generated. • Section 13, References: Updated list of references. |

TABLE OF CONTENTS

| | |
|---|-----------|
| LIST OF ABBREVIATIONS | V |
| 1. INTRODUCTION | 7 |
| 2. STUDY OBJECTIVES AND ENDPOINTS..... | 7 |
| 3. INVESTIGATIONAL PLAN | 9 |
| 3.1. OVERALL STUDY DESIGN AND PLAN | 9 |
| 3.2. IMPLEMENTATION OF THE N-CRM MODEL | 9 |
| 3.2.1. CANDIDATE DOSES | 10 |
| 3.2.2. DEFINITION OF A DOSE LIMITING TOXICITY | 10 |
| 3.2.3. DEFINITION OF THE MAXIMUM TOLERATED DOSE | 10 |
| 3.2.4. TARGET TOXICITY RATE | 10 |
| 3.2.5. ESCALATION RULE | 10 |
| 3.2.6. N-CRM STOPPING RULES..... | 10 |
| 3.2.7. DOSE-TOXICITY MODEL..... | 11 |
| 3.2.8. NUMBER OF TOXICITIES REQUIRED BEFORE ALL DOSES ARE CONSIDERED UNSAFE | 11 |
| 3.2.9. COHORT SIZE..... | 12 |
| 3.2.10. OTHER CLARIFICATIONS..... | 12 |
| 3.3. TREATMENTS..... | 12 |
| 4. GENERAL STATISTICAL CONSIDERATIONS | 13 |
| 4.1. BASELINE AND CHANGE FROM BASELINE..... | 13 |
| 4.1.1. UREAGENESIS BASELINE | 13 |

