Thus, there remains a significant unmet medical need for a treatment that allows for sustained ammonia management, prevention of HAC, and risk of neurological damage associated with OTC deficiency.

This statistical analysis plan (SAP) is based on the clinical study protocol 301OTC01, Amendment 5 dated 25th of February 2020 and its associated electronic case report forms (eCRF). This document describes the rules and conventions to be used in the dose selection, analysis and representation of safety and efficacy data as presented in the clinical protocol.

2. Study Objectives and Endpoints

The study objectives and endpoints are presented in Table 2-1.

Table 2–1 Study Objectives and Endpoints

| Objective | Endpoint |
|--|---|
| Primary | |
| To determine the safety of single IV doses of DTX301 in adults with late-onset OTC deficiency. | The incidence of AEs, TEAEs, and SAEs for each dosing cohort, assessed by severity and relationship to study product. |

| Secondary | |
|---|--|
| To establish a dose of DTX301 that has a meaningful increase in the rate of ureagenesis to allow further clinical development. | The change from baseline in the rate of ureagenesis (as measured by the generation of [¹³ C]urea over 4 hours) as determined by gas chromatography mass spectrometry over time to 52 weeks after the IV administration of DTX301. |
| To evaluate the efficacy of single IV doses of DTX301 in adults with late-onset OTC deficiency in the setting of tapering or discontinuing ammonia scavenger medications. | The change from baseline (Day 0) in plasma ammonia area under the curve from time zero to 24 hours (AUC ₀₋₂₄) over time to 52 weeks after IV administration of DTX301 in the setting of tapering or discontinuing ammonia scavenger medications. |
| Exploratory | |
| To assess the impact of DTX301, by dose, on the number of hyperammonemic crises during the study. | The number of hyperammonemic crises observed for each dose over time to 52 weeks after IV administration of DTX301. |
| To evaluate the effect of DTX301, by dose, on urinary orotic acid levels. | The change from baseline in urinary orotic acid excretion over time to 52 weeks after IV administration of DTX301. |
| To evaluate the effect of DTX301, by dose, on plasma glutamine and glutamate levels. | The change from baseline in plasma glutamine and glutamate over time to 52 weeks after IV administration of DTX301. |

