8.1. Rate of Ureagenesis

This efficacy endpoint is defined as the change from baseline in rate of ureagenesis measured by the generation of ¹³C-urea over 4 hours as determined by isotope ratio mass spectrometry at Weeks 6, 12, 20, 24, Early Withdrawal, and End of Study (Week 52). The observed, change from baseline, and percent change from baseline in rate of ureagenesis will be summarized by DTX301 dose/prophylactic corticosteroids and visit based on the SS.

Rate of ureagenesis ($\mu\text{mol}\cdot\text{h}/\text{kg}$) for a given patient at a specific visit will be estimated using the following steps:

[REDACTED]

The association between change from baseline in rate of ureagenesis and DTX301 dose (2.0×10^{12} GC/kg, 6.0×10^{12} GC/kg and 1.0×10^{13} GC/kg) will be evaluated [REDACTED]

[REDACTED]

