8.2. Plasma Ammonia Area Under the Curve from Time Zero to 24 Hours

This efficacy endpoint is defined as change from baseline in the AUC_{0-24h} of plasma ammonia at Weeks 6, 12, 24, Early Withdrawal, and End of Study (Week 52). Two samples will be collected at each visit and timepoint. One sample will be processed by the local laboratory and one sample will be processed by the central laboratory. The observed, change from baseline, and percent change from baseline in the AUC_{0-24h} of plasma ammonia will be summarized by category (i.e. central laboratory vs. local laboratory), DTX301 dose/prophylactic corticosteroids, and visit based on the SS. Change from baseline in the AUC_{0-24h} of plasma ammonia will be analyzed [redacted] [redacted] used for change from baseline in rate of ureagenesis based on the SS.

The baseline for the AUC_{0-24h} measurement is based on the hourly plasma ammonia results beginning on Day 0 and ending on Day 1 prior to DTX301 administration. AUC_{0-24h} will be calculated [redacted]

[redacted]

[redacted]

[redacted]

The rules for handling of missing data for the AUC_{0-24h} calculation are described in the [Appendices](#).

The plasma ammonia listing and summary will also include the time-normalized AUC_{0-24h} , calculated [redacted]

[REDACTED]

The following additional summary statistics will be provided (overall, by DTX301 dose/prophylactic corticosteroids and for Cohorts 3 and 4 combined) for both AUC_{0-24h} and time-normalized AUC_{0-24h} of plasma ammonia by visit: geometric mean, coefficient of variation (CV) %, geometric CV%. The mean and the standard deviation will also be provided for the logarithmic transformation of both AUC_{0-24h} and time-normalized AUC_{0-24h} of plasma ammonia.

An additional linear mixed model for repeated measures will provide a comparison of the

[REDACTED]

A longitudinal plot of plasma ammonia (as determined by central lab) will be provided by subject, including the display of the AUC_{0-24h} for the subject alongside each plot.

A longitudinal plot of plasma ammonia AUC_{0-24h} (as determined by central lab), alanine aminotransferase (ALT) level (as determined by central lab for both scheduled and unscheduled visits), and corticosteroid regimen (prednisone/prednisolone) over time (each dose taken at the visit and possibly dose modifications in-between) will also be provided by subject.

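### SAP 4.10 calls every unadjusted efficacy p-value of 0.05 or less statistically significant, over up to five visits and three doses, with no readable deciding contrast and no nominal label

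*SAP*

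**What the plan says.** SAP 4.10 sets a rule for the whole plan. Unless another section specifies otherwise, "all testing of statistical significance will be 2-sided" and "all p-values less than or equal to 0.05 will be considered statistically significant". SAP 4.5 adds: "No formal adjustment for multiplicity will be performed".

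The safety analyses are descriptive (Protocol 10.5.3.1), so the rule bears mainly on efficacy. SAP 8.1 defines the ureagenesis endpoint as change from baseline "at Weeks 6, 12, 20, 24, Early Withdrawal, and End of Study (Week 52"), and SAP 8.2 defines the ammonia endpoint as change from baseline in the AUC of "plasma ammonia at Weeks 6, 12, 24, Early Withdrawal, and End of Study (Week 52"). SAP 3.3 models efficacy by dose with Cohorts 3 and 4 combined, which gives three dose groups.

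The paragraphs that specify the models in 8.1 and 8.2 are redacted. The SAP version history indicates what they produce. For ureagenesis, the Version 3.0 entry says "MMRM outputs will include estimates for between-DTX301 dose (overall and by visit) comparisons". For log-transformed ammonia AUC, the Version 4.0 entry describes a comparison "for each DTX301 dose vs the lowest dose and at each visit vs Baseline".

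Neither secondary endpoint is called exploratory; SAP 8.3 keeps that heading for other measures. The objective attached to ureagenesis is "To establish a dose of DTX301 that has a meaningful increase in the rate of ureagenesis to allow further clinical development" (SAP 2, Table 2-1).

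**The concern.** Leaving p-values unadjusted is ordinary in a Phase 1/2 study. The difficulty is doing so while also declaring each one that reaches 0.05 statistically significant, with no readable statement of which visit, dose or comparison answers each secondary objective. Followed as written, the plan allows one dose-by-visit cell, from a trial of about 11 treated subjects, to be reported as a significant effect or a significant difference between doses. What is at stake is how an isolated efficacy result may be described in the study report.

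**Working it through.** **The plan's own figure.** The 0.05 in SAP 4.10 is an input, not a derived quantity. For a single test, 1 − 0.95 = 0.05. No family-wise rate or power is stated, and SAP 4.9 says that the sample size does not come from a power calculation.

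**Inputs from the documents**
- Scheduled post-baseline visits: 5 for ureagenesis (SAP 8.1) and 4 for ammonia (SAP 8.2), so 9 endpoint-visit combinations.
- Dose groups: 3 (SAP 3.3).
- Subjects: 9 enrolled at Amendment 5 (Protocol 15.3.5), plus 2 in Cohort 4 (SAP 3.1), so 11.

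**Assumptions**
- The 11 subjects split 3, 3 and 5: three in each of Cohorts 1 to 3, Cohort 4 added to the top dose, and no Cohort 3 expansion.
- Normal data, no true effect, and the two endpoints independent of each other.
- Correlation between visits from 0 to 0.9. The documents give no value.
- A separate t test for each cell, with variance pooled over doses (11 − 3 = 8 df). This stands in for the redacted repeated-measures model.

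**Candidate families of tests**
- A: all pairs of doses at each visit: 3 × 5 + 3 × 4 = 27.
- B: change from baseline for each dose at each visit: 3 × 9 = 27.
- C: change from baseline at 1.0 × 10^13 GC/kg only: 9.

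**Independence bound.** P(at least one p ≤ 0.05) = 1 − 0.95^k. For k = 27 this is 0.750, and for k = 9 it is 0.370. Counting only favourable results, 1 − 0.975^27 = 0.495 and 1 − 0.975^9 = 0.204.

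**Simulated chance of at least one p ≤ 0.05 under no effect**

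| Visit correlation | A, either direction | B, either direction | B, favourable only | C, either direction |
|---|---|---|---|---|
| 0 | 0.65 | 0.72 | 0.48 | 0.37 |
| 0.5 | 0.58 | 0.65 | 0.41 | 0.32 |
| 0.8 | 0.46 | 0.52 | 0.32 | 0.24 |
| 0.9 | 0.39 | 0.45 | 0.27 | 0.20 |

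For C in the favourable direction only, the range is about 0.10 to 0.21. Repeat runs agree to within about 0.01.

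**Sensitivity**
- Correlation between endpoints lowers the rates modestly. For B, visit correlation 0.9 with endpoint correlation 0.5 gives 0.42 (0.25 favourable).
- Sample size hardly matters. With 3, 3 and 12 subjects (the maximum of 18), B runs from 0.73 at correlation 0 to 0.45 at 0.9.
- Changes that share a baseline are already correlated. With independent, equal-variance errors, each change has variance 2σ² and any two have covariance σ², so the correlation is 0.5. The rows from 0.5 down are therefore the better guide.

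**The case against.** The strongest case against has five parts.

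1. **The 0.05 is a per-test level, and the lack of adjustment is disclosed.** This stands. A reader might infer that the plan promises a 5% chance of a false efficacy claim and breaks that promise. Neither document states such a rate, so no stated guarantee is broken.

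2. **The size depends on assumptions.** This stands too. A reader might infer that a false positive is more likely than not, or that a single multiplier of 5% applies. Family A falls below one half at correlations of 0.8 and 0.9, family C is below one half throughout, and the favourable-only rates are below one half throughout. A two-sided count also includes results against the drug, and in family A it includes a lower dose looking better. Only ranges are supportable.

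3. **The model text is redacted.** A deciding contrast could sit in the hidden paragraphs, and SAP 4.10 allows exceptions stated elsewhere. The version history speaks of estimates, and for log ammonia it describes comparisons with the lowest dose and with baseline, not every pair at every visit. So neither the test count nor the absence of a named contrast can be confirmed. Separate local-laboratory ammonia results are readable only as summaries and are not counted here.

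4. **No p-value selects the dose.** A reader might infer from the ureagenesis objective that an isolated significant cell would choose the dose. No passage says so. Protocol 10.5.1 defines the optimal biological dose by predicted toxicity, the ureagenesis target is a magnitude (about 300 μmol/kg/hr ± 10%), cohort progression goes through the data monitoring committee, and SAP 3.1 records the dose as already declared with Cohort 3.

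5. **This is an early-phase, single-arm study with a safety primary endpoint.** True, and no confirmatory error control is lost. But that context argues for calling the p-values nominal, which the readable text does not do.

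None of these removes the rule in SAP 4.10, which is readable, general and unqualified for the efficacy analyses.

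**Conclusion.** The point holds as a labelling defect. SAP 4.10 and 4.5 together let any one unadjusted efficacy p-value of 0.05 or less be called statistically significant, while the secondary endpoints span 5 and 4 visits at three doses.

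Under the assumptions above, the chance of at least one such result with no true effect is about:
- 40% to 65% for 27 by-visit between-dose tests;
- 45% to 70% for 27 dose-by-visit changes from baseline (25% to 50% favourable);
- 20% to 38% for the changes at 1.0 × 10^13 GC/kg alone (10% to 21% favourable).

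The family size and the correlations are assumed, because the model text is redacted and no correlation is given. Even the narrowest family is well above the per-test level. This is a cheap improvement that should be made; it does not invalidate the design.

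**What to change.** In SAP 4.10, replace the significance rule for efficacy with: 'p-values and 95% CIs for efficacy are nominal and descriptive; no efficacy result will be described as statistically significant on the basis of an unadjusted p-value.' Say the same in SAP 4.5, next to the statement that no adjustment is made.

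The label is enough by itself. Naming a deciding contrast now is not advised: the study is open-label and SAP Version 4.0 is dated November 2021, after Cohort 4 enrolment had closed, so the choice would follow data already accrued.

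The cost is two or three sentences, with no new data, models or subjects. The small downside is that the sponsor can no longer call an isolated dose-by-visit p-value of 0.05 or less statistically significant.
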